2.2.4 System Software

Data processing software reconstructs images from the raw data, re-processes reconstructed image data, and/or enables improved visualization of the image data. Data processing software may also be used to calculate quantitative physiologic measurements, such as blood flow rates and tissue stiffness.

2.3 Accessory and Ancillary Devices

Accessory devices can be used optionally along with systems under study. Some accessories are intended to be included with the device system upon commercialization and others may be separately marketed. Accessories include devices such as gels/coupling agents and hardware/software components may be used, as described in the following sections. A variety of accessory devices and combinations of accessory devices not specifically listed in

Study Title: Development Of Medical Ultrasound Systems, Accessories, And

Components - GE Bangalore

Study Number: 110.08-2015-GES-0004

this protocol may or may not be used, at the discretion of the study staff. Other routine ancillary equipment may be used as necessary to accomplish research objectives.

2.3.1 Coupling Agents (Gels, Lotions, and Water Baths)

When handheld probes and some automated probes are used, a layer of water based gel or lotion (i.e. coupling agent) is placed between the probe and the subject to eliminate air bubbles and aid in moving the probe along the subject. The gel transmits the sound beam from the probe to the subject without a significant loss of power.

2.3.2 Accessory Hardware and Software

Development efforts will also be focused on other types of system accessory hardware and software components such as but not limited to the scanner user interface, tracking equipment, and physiologic monitoring tools (non-life supporting or sustaining) such as an electrocardiogram (ECG). In some cases, probes may be coupled with accessories as necessary for testing.

2.3.3 Intended Use/Purpose of the Research Device

In clinical settings, when prescribed by a medical doctor, the non-invasive ultrasound systems are intended to provide information to medically trained personnel to use during the diagnosis process. Diverse devices may be used in this study in accordance with their labeled indications or in new ways. The indications may vary between devices. The procedures conducted in this study are intended for research purposes and are not intended as a substitute for required medical care.

2.4 Regulatory Status

This study may include devices, components and accessories that are post-market (completely through the Quality System and approved for commercial use in India), pre-market (investigational and not completely through the entirety of the Quality System or not in accordance with labeled indications in India), and in some cases a combination of a post-market devices, accessories or components and an investigational device, accessory or component. All activities will be considered investigational.

2.5 Device Classification and Rationale

Indian medical device classifications distinguish low to medium risk devices such as diagnostic ultrasound devices as Class B devices on a Class A (low risk) – D (highest risk) scale. The regulatory procedures for medical devices vary according to their class. In general, higher-risk devices are subject to more regulation in India. Presently there are no Indian requirements for registration of diagnostic ultrasound products prior to commercialization. The Declaration of Helsinki and principles of ISO 14155:2011 and the India Ministry of Health and Family Welfare (MOHFW) will be employed in this study.

Study Title: Development Of Medical Ultrasound Systems, Accessories, And

Components - GE Bangalore

Study Number: 110.08-2015-GES-0004

2.6 Device Accountability and Maintenance

2.6.1 Device Issuance, Installation, and Accountability

Verification and documentation of device safety, traceability of software versions, device labeling, and device installation/disposition will be recorded by the site. Unique identifying information (e.g. model, serial number, etc.) of each device used in this study will be recorded. Devices that are concurrently used in other product development or research activities will be qualified for use in this study prior to being used in subject procedures.

2.6.2 Device Security and Access

Devices for this study will be located at a GEHC facility. GEHC facilities are restricted to GEHC employees or GEHC contractors, or persons supervised by a GE employee or an authorized GE Contractor. The devices that are part of this study will be managed per specific local safety procedures.

2.6.3 Maintenance and Optimization of Study Devices

The devices are frequently upgraded and/or modified during the course of development.

2.6.4 Concurrent Use of Research Devices and Research Area

Research device(s) and their accessories and components as well as the research area containing these devices may be used for other concurrent research activities and other activities authorized by the Sponsor, in accordance with the Sponsor's procedures and applicable laws and regulation. Procedures conducted in this study are done to accomplish research objectives outlined in the aims of this protocol, and are not intended to provide diagnostic information. No study scans will be conducted in this study solely for commercial training or product demonstration purposes.

2.6.5 Labeling of Research Devices

Investigational systems used in this study will be clearly labeled as investigational devices, in accordance with applicable US FDA labeling and/or regional regulatory requirements in India. Device qualification history will be maintained by GE, including information such as when devices are installed for study use.

2.6.6 Disposition of Devices

Devices will be dispositioned by GE in accordance with applicable local laws and regulations.

3. OBJECTIVES OF RESEARCH STUDY

3.1 Purpose of the Study

Ultrasound device systems, accessories, and components can be used to successfully perform ultrasound scans resulting in data from human subjects. No efficacy tests will be performed for any clinical indication as part of this study, and no statistical hypothesis testing or other cohort-based statistical inferences are prospectively planned.

3.2 Study Objectives

This study includes a diverse series of iterative ultrasound scans performed to satisfy specific aims outlined in this protocol. These aims include a variety of scan evaluations such as usability, ergonomics, and workflow, from pre-

Study Title: Development Of Medical Ultrasound Systems, Accessories, And

Components - GE Bangalore

Study Number: 110.08-2015-GES-0004

market and post-market device systems, accessories, and components, and combinations thereof. Information learned is primarily intended for engineering optimization and complaint investigations.

3.3 Study Endpoints

3.3.1 Primary Endpoint

The primary endpoint is number and type of ultrasound study scans (which may include one or more sets of data and/or image data), which does not include evaluation of any specific clinical condition or efficacy measures.

3.3.2 Safety Endpoints

The number and type of safety issues, including adverse events (AEs) and serious adverse events (SAEs) will be reported. The number and type of device complaints will be reported.

4. DESIGN OF RESEARCH STUDY

4.1 Type of Research Study

This is an open label, prospective research study involving human subjects. Due to the heterogeneous nature of these diverse study scans, there will be no cohort-based comparative efficacy or safety analysis and no assessment of missing data elements (it is not required that any study scan produce all exploratory elements) and therefore no randomization. Prospective subjects are enrolled and then undergo one or more study scans without randomization, stratification, block/quota, or other grouping.

4.2 Controls and Minimization of Bias

This study is open to the general population. All who respond to IRB/EC-approved recruitment materials and meet all of the inclusion criteria and none of the exclusion criteria are eligible to be enrolled. This minimized possible selection bias. Based on the study hypotheses and Aims, employing control or comparison groups and techniques to reduce potential source of bias are not indicated. The data derived from this study are not intended to yield any cohort-based safety or efficacy conclusions for regulatory purposes. Anonymized images resulting from this study may be used for regulatory support purposes if they are used as samples or examples to demonstrate image quality only.

5. SUBJECTS

5.1 Study Population

This population will consist of adult men and women that meet all inclusion criteria and do not meet any exclusion criteria. The term "adult" shall mean any individual 18 years of age or older.

Subjects in this study will generally reflect the desired population for the device use. Because different anatomical components of the human body have different acoustic properties, it is prospectively expected that the study will

Study Title: Development Of Medical Ultrasound Systems, Accessories, And

Components - GE Bangalore

Study Number: 110.08-2015-GES-0004

enroll a diverse population with variant body habitus in order to assess performance in different sub-populations (such as different gender, age, or body type).

5.2 Number of Subjects

This study will be conducted at a single site and will enroll up to 150 subjects over the 5 year duration. Based on the Sponsor's prior research and engineering experience, this number of subjects represents the minimum needed to adequately evaluate each system, probe, feature and/or application setting in a sample of different subjects that sufficiently represents the intended population of device use. Only the minimum number of study scans necessary to accomplish research aims will be performed, which may be fewer than the total number allowable by this protocol.

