Regulatory Status:	This study will conduct procedures using non-invasive ultrasound devices, accessories, or components that are pre-market (investigational), post-market (commercially available), or commercial but modified with investigational hardware and/or software components. No therapeutic ultrasound devices will be used. These devices share a common and well-understood safety profile. All scanning conducted is for research purposes only, and all procedures are treated as investigational (not for use in medical management).

Procedures/ Methods:	Subjects will be considered enrolled that provide written informed consent to participate, and with thereafter be scheduled to attend up to up to five (5) ultrasound scans per day lasting up to 60 cumulative minutes each with approximately a 15 minute break before starting another study scan (limited to 15 cumulative minutes of scan time per eye, per day for ophthalmic scanning) as long as they remain eligible per the study inclusion and eligibility criteria. Vital sign information about subjects may be collected and subjects will be positioned for scanning of a variety of target anatomic areas using a variety of non-invasive, transcutaneous techniques, such as scanning abdominal, musculoskeletal, breast(s), peripleural, transcranial, cervical/neck, cardiac, ophthalmic, vascular, extremity, soft tissue, and other accessible anatomical regions. The subject will be monitored for adverse events throughout the research study scan. The resultant images and associated data will be recorded and stored as part of study data.
Sample Size and Sites:	This study will be conducted at a single site and will enroll up to 150 subjects over the approximate 5 year duration. Based on the Sponsor's prior research and engineering experience, this number of subjects represents the minimum needed to adequately evaluate each system, probe, feature and/or application setting in a sample of different subjects that sufficiently represents the intended population of device use. Only the minimum number of study scans necessary to accomplish research aims will be performed, which may be fewer than the total number allowable by this protocol.
Study duration:	
The study is expected to last approximately 5 years.
 
Estimated start date: 15/Aug/2016
 
Estimated end date: 15/Aug/2021

Study Title: Development Of Medical Ultrasound Systems, Accessories, And

Components - GE Bangalore

Study Number: 110.08-2015-GES-0004

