8.3 Sample Size Justification

The sample size is not designed to test any statistically powered endpoint and is determined based on the engineering development needs of the Sponsor. Due to the heterogeneous nature of the study procedures, each subject will be allowed to participate multiple times, if he/she remains eligible per protocol requirements. As possible, the minimum number of study scans will be conducted to meet the internal engineering and optimization needs of the Sponsor, and it is prospectively planned that significantly fewer subjects (fewer study scans) than the maximum may be enrolled, if possible to achieve study aims.

Study Title: Development Of Medical Ultrasound Systems, Accessories, And

Components - GE Bangalore

Study Number: 110.08-2015-GES-0004

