10.5 Early Termination/Suspension of the Study

The Sponsor may terminate the study prematurely according to certain circumstances. Examples of such circumstances include ethical concerns, insufficient participant recruitment, participant safety concerns, alterations in accepted clinical practice that make the continuation of a clinical trial unwise, early evidence of benefit or harm of the research product, or for any other reason.

The Sponsor will promptly notify the investigators of any determination to terminate the study outside of the protocol timeframe. The Sponsor will provide each investigator with written guidelines/instructions on termination processes and timelines.

The site is responsible for reporting the early termination to the responsible EC/IRB, per their policy.

Study Title: Development Of Medical Ultrasound Systems, Accessories, And

Components - GE Bangalore

Study Number: 110.08-2015-GES-0004

11.QUALITY ASSURANCE AND CONTROL

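### Does calling 150 both the enrolment ceiling and the minimum needed leave the study without a usable sample size?

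*Protocol*

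**What the plan says.** The synopsis states that the study "will enroll up to 150 subjects over the approximate 5 year duration", and section 5.2 that it "will enroll up to 150 subjects over the 5 year duration". Both then give the same rationale, based on the sponsor's experience: "this number of subjects represents the minimum needed to adequately evaluate each system, probe, feature and/or application setting", in subjects who represent the intended users of the device. Both close with a restraint on scanning: "Only the minimum number of study scans necessary to accomplish research aims will be performed", and they add that this may come to less than the protocol permits.

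Section 8.3 sets out the basis of the number: "The sample size is not designed to test any statistically powered endpoint and is determined based on the engineering development needs of the Sponsor". It then says that "it is prospectively planned that significantly fewer subjects (fewer study scans) than the maximum may be enrolled, if possible to achieve study aims". Section 3.1 states that "no statistical hypothesis testing or other cohort-based statistical inferences are prospectively planned". Section 10.5, on early termination, says "Examples of such circumstances include ethical concerns, insufficient participant recruitment, participant safety concerns", among others, and ends with an open-ended clause that leaves the sponsor free to stop on any ground.

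**The concern.** A ceiling and a floor at the same value leave exactly one total that satisfies both. The rationale in the synopsis and 5.2 implies that evaluation with fewer than 150 subjects is inadequate. Section 8.3 implies that it can be adequate. A reader who takes 5.2 at its word would call any lower total a shortfall; a reader of 8.3 would call it an acceptable outcome.

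In a confirmatory trial this would matter. A target, a minimum evaluable number and a cap are different things, and confusing them can change power, the stopping of recruitment and the reading of a short study. Section 10.5 seems to raise the stakes, because it names poor recruitment as a possible reason to end the study and 150 is the only enrolment figure in the document. An ethics committee might also want to know whether 150 volunteers are required or only allowed, since they are employees or contractors of the sponsor's parent company.

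**Working it through.** **Can 150 be derived?** No. The protocol gives no significance level, power, effect size, variance, precision target, number of devices or number of subjects per device. The figure cannot be reproduced, and 8.3 does not claim that it can be: it rests on engineering need. The check is therefore a comparison of statements.

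**The statements side by side**, with N the number enrolled:

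| Place | Statement about N | Kind of statement |
|---|---|---|
| Synopsis, 5.2 (first sentence) | N ≤ 150 | operating limit |
| Synopsis, 5.2 (second sentence) | N ≥ 150 for adequate evaluation | rationale |
| Synopsis, 5.2 (last sentence) | no more scans than the aims need | operating limit |
| 8.3 | N < 150 allowed if the aims can be met | conditional permission |

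The first two rows together give N = 150 only, which clashes with the fourth. So the inconsistency is real. It lies between a sentence of justification and the operating statements; the operating statements do not conflict with one another.

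**Does the clash change what anyone does?** There are three possible situations.

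1. *The aims are met before 150 subjects.* Section 8.3 permits stopping, and the last sentence of 5.2 allows no scans beyond those needed. The second sentence of 5.2 would call the evaluation inadequate, but it does not instruct anyone to go on enrolling.
2. *The aims are not yet met and N is below 150.* Enrolment may continue, whether 150 is read as a floor or as a cap.
3. *N reaches 150.* Enrolment stops on either reading.

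Conduct is the same in all three.

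**Does it change the results?** The primary endpoint (3.3.1) is the number and type of scans. Safety reporting (3.3.2, 8.1) consists of counts, listings and narratives. Descriptive statistics are optional (8.2). None of these uses 150 as a denominator, threshold or information target.

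**Does 10.5 turn on 150?** It does not mention the figure. Recruitment is one example in a list that ends by leaving the sponsor full discretion, so no decision rule depends on which reading is right.

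**The case for a change.** The case for changing the text is that the contradiction stands in the current wording and is cheap to remove. The condition in 8.3 does not dissolve it, because allowing fewer subjects if the aims are met presupposes that they can be met with fewer, which the rationale denies. The closing sentence of 5.2 limits scans, and since one subject may be scanned many times, scans and subjects are not the same thing. Moreover, enrolment is counted at consent (5.8) while eligibility is verified afterwards (5.7), so a single screen failure would leave fewer than 150 scannable subjects. A minimum equal to the cap has no margin.

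The first point stands: the phrase is wrong as literally written. The others carry less weight. Section 8.3 itself places fewer scans in parentheses after fewer subjects, so the protocol treats the two as linked. There is also a natural reading of the disputed sentence, which is that the cap was set no higher than the sponsor expects full coverage of an open-ended device list (2.1) to need. The text does not spell this out, but the reading fits both 5.2 and 8.3. The screen-failure point would matter only if some analysis required 150 evaluable subjects, and none does. As for the ethics committee, the limit on the number of people exposed is 150 on every reading, and 8.3 already says that fewer may suffice.

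**Conclusion.** The wording conflict is genuine, but it is a drafting slip in a rationale, and correcting it would gain nothing for the conduct or conclusions of the study. Its size is zero in every quantity that a sample-size error normally affects: there is no power or error rate to disturb, the cap stays at 150, the endpoint is a tally of whatever scans are done, and no stopping or reporting rule refers to the figure. Section 8.3, the section devoted to sample size, already holds the workable position that 150 is a maximum and fewer is acceptable if the aims are met; it permits a lower total and does not commit the study to one.

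This rests on two assumptions: that staff follow the operating statements in 5.2 and 8.3, and that no analysis plan outside this document attaches a required number of evaluable subjects to 150. The protocol's statement that no inferential analysis is planned makes the second a safe assumption.

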5.7 Screening Subjects for Enrollment

Subjects may be pre-screened via telephone or email following IRB/EC-approved scripts to assess potential eligibility.

Informed consent will be obtained as described in the Informed Consent and Privacy Requirements section. Upon agreeing to participate in the Study, the subject will sign and date the ICF. The subject will be assigned an identification code unique to the subject (i.e. next sequential number on the enrollment log). A subject's enrollment in the study begins when he/she completes the above Informed Consent process and is assigned a unique study identification code.

Study Title: Development Of Medical Ultrasound Systems, Accessories, And

Components - GE Bangalore

Study Number: 110.08-2015-GES-0004

After the subject has completed the informed consent process, Study Staff will verify that he or she meets all of the inclusion criteria and none of the exclusion criteria. Determination of eligibility relies on information reported by the subject. The Study Staff may or may not have necessary medical training or licensure to confirm subject self-reported health status and will not make independent assessments.

Subjects may participate more than once throughout the study's duration. Eligibility will be documented at the subject's first visit, and for any subsequent visits it will be confirmed that the subject remains eligible per the inclusion/exclusion criteria prior to the study scan.

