6. STUDY PROCEDURES

6.1 Protections and Safeguards

Participation in Multiple Study Visits – Enrolled subjects may be eligible for one or more research study visit. The Investigator or study staff may limit the number or duration of visits for any subject if it is suspected that the subject is under undue influence to participate, if participating could pose a risk to the subject's physical or mental

Study Title: Development Of Medical Ultrasound Systems, Accessories, And

Components - GE Bangalore

Study Number: 110.08-2015-GES-0004

health, or for any other reason, in the opinion of the study staff. Subjects that have already been screened for enrollment, provided consent, and undergone necessary safety and eligibility screening to participate may participate in additional study visits if the subject:

- has provided written informed consent using the current IRB/EC-approved consent version (subjects should be re-consented if previously consented using an older version of the consent form).
- remains eligible according to the inclusion/exclusion criteria on the day of the procedure.

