6.1.3 Activities during a Study Scan

Each subject may elect to participate in up to five (5) study scans per day lasting up to 60 cumulative minutes each with approximately a 15 minute break before starting another study scan. Ophthalmic scanning will be limited to no more than 15 cumulative minutes of scan time per eye, per day.

The start time of a study scan begins when the device contacts the subject's skin and scanning begins; the stop time is when the study scan is complete. Pauses in active scanning are not counted towards the cumulative scan duration.

The study ultrasound scan will be performed while the subject is lying, sitting, or standing. Subjects may be asked to shift positions, to hold still, complete breath hold(s), bear down (Valsalva maneuver), or other maneuvers necessary for the scanning procedure. In some cases, device accessories (e.g. coupling agents, probe, land marking, tracking, monitoring, or other ultrasound device components) may be placed in direct contact with the subject's skin and/or superficial marks may be placed with a semi-permanent medical grade marker.

Scanning may be performed for target anatomic areas using a variety of non-invasive, transcutaneous techniques, such as scanning abdominal, musculoskeletal, breast(s), peripleural, transcranial, ophthalmic, cervical/neck, cardiac, vascular, extremity, soft tissue, and other accessible anatomical regions. More than one region may be scanned in a single study scan.

Study Title: Development Of Medical Ultrasound Systems, Accessories, And Components - GE Bangalore

Study Number: 110.08-2015-GES-0004

If a subject reports discomfort or wishes to stop the scan for any reason, the Study Staff will respond to subject's concerns and adjust the scanning procedures or, if the concern is not able to be resolved, discontinue the study scan. There will be no negative repercussions to the subject for reporting discomfort or deciding to stop the study scan, and he/she may still participate in future visits. Non-medical care will be provided to the subject to alleviate any discomfort, as needed.

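### Does the sample-size text need a stated maximum number of scans, given that the scan count is the primary endpoint?

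*Protocol*

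**What the plan says.** The study may enrol up to 150 subjects at one site over about 5 years (Synopsis, Sample Size and Sites; Section 5.2). Both places promise to limit scanning to what the aims require and add that the scans performed are a number "which may be fewer than the total number allowable by this protocol". Both also say of the 150 that "this number of subjects represents the minimum needed to adequately evaluate each system".

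Section 8.3 says the size follows the Sponsor's engineering needs and tests no powered endpoint. It adds that "each subject will be allowed to participate multiple times, if he/she remains eligible per protocol requirements", and that "it is prospectively planned that significantly fewer subjects (fewer study scans) than the maximum may be enrolled".

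The limits on scanning are elsewhere. Section 6.1.3 states: "Each subject may elect to participate in up to five (5) study scans per day", with limits on minutes per scan and per eye. Section 5.7 allows repeat participation ("Subjects may participate more than once throughout" the study). Section 6.1 gives discretion without a number: "The Investigator or study staff may limit the number or duration of visits for any subject". Section 3.3.1 defines the outcome: "The primary endpoint is number and type of ultrasound study scans".

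**The concern.** A reader who meets a reference to a total allowed by the protocol expects to find that total in the protocol, and it is not there. The reference is to the protocol itself, so the figure has not been left to another document. The scan is also the unit of the primary endpoint, while the only study-wide number is in subjects.

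Section 8.3 makes this worse by bracketing fewer scans with fewer subjects straight after allowing each subject to take part repeatedly. With repeat visits, the number of subjects can fall while the number of scans rises. The volunteers are employees or contractors of the Sponsor's group, so a statement that reads as reassurance about exposure ought to be checkable by the ethics committee and the monitor. If the reference pointed to nothing and conduct depended on it, oversight of the scan count would be weakened.

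**Working it through.** **Is there a figure to reproduce?** No. The protocol states no scan total, and no power formula applies because no hypothesis test is planned (Sections 3.1 and 8.3). The check is whether a total follows from the stated limits, and whether anything depends on it.

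**Inputs**
- Subjects: at most 150 (Section 5.2).
- Scans per subject per day: at most 5 (Section 6.1.3).
- Duration: 15/Aug/2016 to 15/Aug/2021 (Synopsis), which is 5 x 365 + 1 leap day = 1,826 days. Both dates are estimates.
- Scan days per subject, D: one or more, with no upper number (Sections 5.7, 6.1, 8.3).

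**Formula:** total scans = 150 x 5 x D = 750 x D.

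| Scan days per subject, D | Basis | Total scans |
|---|---|---|
| 1 | assumed | 750 |
| 12 | assumed | 9,000 |
| 60 | assumed (monthly for 5 years) | 45,000 |
| 1,250 | assumed 250 working days a year x 5 years | 937,500 |
| 1,826 | every calendar day | 1,369,500 |

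The last row is 5 x 1,826 = 9,130 scans per subject. A ceiling can therefore be derived, but it requires every subject to be scanned five times on every day of the study. It is formally a limit and restrains nothing.

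**Fewer subjects against fewer scans.** Under assumed visit counts, 75 subjects x 5 x 12 = 4,500 scans, against 150 x 5 x 1 = 750. Half the subjects give 4,500 / 750 = 6 times the scans. This confirms that the two quantities can move in opposite directions. The factor of 6 comes entirely from the chosen visit numbers.

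**What Section 8.3 most naturally means.** Its verb is to enrol, and subjects are enrolled while scans are not. The maximum it refers to is therefore best read as the 150 subjects. The first half of the same sentence separately commits to conducting as few scans as the engineering needs allow. A plan that cut subjects and raised scans beyond need would still breach that commitment.

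**Is the count tracked without a cap?** Section 6.1.4 requires date, duration, device, region and subject ID for each scan. Section 10.4.1 requires monthly reports of all scans to the Appropriate Authority, with the type and date of each scan. Sections 8 and 8.1 put the number and type of scans in the final report. Section 6.1 lets staff limit visits where undue influence or risk is suspected.

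**What would differ if the wording were changed?**
- Deleting the comparison: the commitment to scan no more than needed stays, and the endpoint, its reporting and the conduct of the study are the same.
- Calling 150 consistently a maximum: every operative statement already treats it as a ceiling.
- Separating subjects from scans in Section 8.3: this makes the sentence clearer and alters no count.

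**The case for a change.** The strongest case for a change is that the text refers to a number that does not exist, in the unit of the primary endpoint, in a sentence meant to reassure. The ceiling that can be derived is so high that the statement would be true of any conduct, so it gives an ethics committee nothing to hold the Sponsor to. Repair would take two or three sentences, and the records needed for a running count are already kept.

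Part of this stands. The comparison carries no information, the bracket in Section 8.3 is loose, and 150 cannot be both an upper limit and the minimum needed when Section 8.3 plans for significantly fewer.

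The inference from poor wording to a fault in the plan does not stand. The comparison is permissive, so nobody is asked to act on it. A descriptive count needs no upper bound to be valid, and what was done can be checked from the scan records and the monthly reports. Adding a study-wide scan limit would be new content. It would restrict iterative engineering work whose volume cannot be known in advance, and might itself need amending later. That is a choice for the Sponsor and the ethics committee.

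**Conclusion.** No change to the plan is called for. The synopsis and Section 5.2 refer to an unquantified scan total, and the ceiling implied by the stated limits (1,369,500 on calendar days, 937,500 at an assumed 250 working days a year) is too loose to act as one. The effect on results is nil: there is no test, no power calculation and no inference about a cohort, and the primary endpoint is whatever count the scan records give.

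The description of 150 as a minimum and the bracket in Section 8.3 are clerical slips, which could be tidied whenever the document is next revised. This conclusion rests on three readings: that the commitment to the fewest scans needed is the operative statement, that the maximum in Section 8.3 means the 150 subjects, and that scans are recorded and reported as Sections 6.1.4, 8, 8.1 and 10.4.1 require.
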